## 2.0 TRIAL DESIGN

Open label phase I trial. Primary objective is to determine the recommended phase 2 dose (RP2D) of the combination of XL888 and pembrolizumab. The design is 3+3 with 3 dose levels of XL888 (X). MTD is defined as the dose at which less than one-third of the subjects experience a DLT in the first 4 weeks of treatment.

After determining the RP2D, an additional 16 patients with pancreatic cancer (Arm A) and 16 patients with colorectal cancer (Arm B) will be enrolled in an expansion phase to confirm toxicity profile and obtain paired biopsies. Paired biopsy performed on 8 patients in each group. Patient selected for biopsy must have a primary or metastatic non-bone site that is amenable to safe biopsy. Bone only lesions are not suitable for biopsy. Patients undergoing paired biopsies will be assigned into two treatment cohorts (8 in each) and treated according to the schema below.

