**Dose level 3 will only be tested if we observe 2 DLT's on dose level 2.**

### 5.2.2 Dose Escalation

Starting dose of 45mg; if  $\geq 2$  patients with DLTs in 3 ( $\geq 2/3$ ) or 6 ( $\geq 2/6$ ) subjects; stop and consider reduced dose of XL888. If not, increase dose to 90 mg and test 3-6 patients. If  $\geq 2$  patients with DLTs in 3 or 6 subjects, reduce dose to 60 mg and try again. If an acceptable dose is identified, treat 16 more patients at the MTD. Prior to dose escalation, we will obtain approval from the Data Safety and Monitoring Committee (DSMC).

**5.2.3 Dose limiting toxicity (DLT)** will be defined as any of the following definitely treatment related adverse events during the first 21 days of therapy:

- Grade IV neutropenia lasting more than 8 days; any neutropenic fever or sepsis;
- Grade III with clinically significant bleeding or any grade IV thrombocytopenia;
- Grade III nausea, vomiting, or diarrhea, lasting  $>72$  hours despite adequate supportive care;
- Other non-hematologic treatment-related toxicity at Grade III or higher
- Grade 4 asymptomatic laboratory abnormalities that last for more than 24 hours or Grade 3 asymptomatic laboratory abnormalities lasting more than 21 days is a DLT.
- Grade IV or higher diarrhea, nausea, vomiting
- In ability to take more than 75% of XL888 due to toxicity.

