#### **7.1.4.2 Treatment Period**

##### **7.1.4.1 Day 1 ( $\pm 3$ days) of each cycle**

- Record concomitant medications
  - Vitals (temperature, HR, BP and RR)
  - History and physical exam, pill diary (prior cycle see section 11.4) and pill count (prior cycle)
  - ECOG performance status
  - Toxicity assessment
  - 12 lead ECG after XL888 administration in cycle 1, cycle 2 and every other cycle
    - Laboratory Assessments

- Hematology hemoglobin, hematocrit, red blood cell count, white blood cell count with differential and platelet count
  - Chemistry sodium, potassium, chloride, bicarbonate, magnesium, calcium, phosphorus, blood urea nitrogen, creatinine, glucose (random), total bilirubin, LDH, total protein, ALP, ALT, AST, and albumin
  - Tumor markers - when applicable
  - Fasting Lipid profile every 3 cycles starting Cycle 4 (i.e C4D1, C7D1, C10D1, C13D1 etc)
  - Urinalysis every 3 cycles starting Cycle 4 (i.e C4D1, C7D1, C11D1 etc)
    - T3, FT4, TSH cycle 2 and then after every 3 cycle
    - For the cycle 1 day 1 labs, blood samples from the screening tests maybe used if completed within 1 week of day 1
- Blood sample 20 cc for correlative work (only cycle 1, 2, 3)
  - Pembrolizumab 200 mg will be administered as a 30 minute IV infusion every 3 weeks. Given the variability of infusion pumps, a window of -5 minutes and +10 minutes is permitted (i.e., infusion time is 30 minutes: -5 min/+10 min).
- XL888 will be administered orally in the infusion center (first dose of each cycle only) prior to pembrolizumab. **(in selected case in patients receiving paired biopsies XL888 will be held in cycle 1)**

#### 7.1.4.2 Days 4, 8, 11, 15 and 18

- XL888 dose administered and diary completed

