## **8.0 STATISTICAL ANALYSIS PLAN**

### **8.1 Determination of Sample Size**

This is a 3+3 standard phase I trial design. The plan is to evaluate two dose cohorts- 45mg and 90 mg. An intermediate dose cohort (60 mg) will be evaluated only if we observe 2 or more DLT's in the 3 or 6 patients enrolled on the 90mg dose. If we observe 2 dose limiting toxicities on dose level 1, then the study will be completed with three patients (minimal number of patients). If we observe two DLT in the first three patients on dose level 1, the study will stop and the principal investigator will discuss at that point whether a lower dose level of XL888 should be tested. If we do not observe any dose limiting toxicities the study will require 9 patients. If we observe one dose limiting toxicity per dose level (maximum number of patient), then the study would require 18 patients. Therefore the phase part sample size can range from 3 to 18 patients. Expansion phase will be started once the recommended phase II dose (RP2D) is determined. Given minimal activity of checkpoint inhibitors in colorectal and pancreatic cancer, an overall response rate of the combination of PD-1 plus HSP90 inhibitor of 20% would be considered clinically significant. With an alpha of 0.1, and power of 80% (relaxed due to the pilot preliminary nature of this proposal) a total of 16 patients should be sufficient to make this determination. We will also obtain biologic endpoints with the paired biopsy samples that can help further develop the combination and understand its role in GI cancers. We plan to enroll 32 patients on the RP2D level with 16 patients per cohort (pancreas and colorectal cancer). Patients in the expansion phase will be assigned to treatment arms by PI (MK-3475 or MK-3475 plus XL-888). After the first 3 weeks all patients will receive the combination therapy. There is no planned comparison between the two arms. The aim of the expansion phase is to confirm the safety profile and tolerability of the regimen in patients with pancreatic and colorectal cancer.

The total number of patients will range from 38 to 50 patients.

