### **8.2 Stopping Rules**

Not Applicable

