## **10.5 Data Management**

The Data and Safety Monitoring Committee (DSMC) of the Winship Cancer Institute will provide oversight for the conduct of this study. The DSMC functions independently within Winship Cancer Institute to conduct internal monitoring functions to ensure that research being conducted by Winship Cancer Institute Investigators produces high-quality scientific data in a manner consistent with good clinical practice (GCP) and appropriate regulations that govern clinical research. Depending on the risk level of the protocol, the DSMC review may occur every 6 months or annually. For studies deemed High Risk, initial study monitoring will occur within 6 months from the date of the first subject accrued, with 2 of the first 5 subjects being reviewed. For studies deemed Moderate Risk, initial study monitoring will occur within 1 year from the date of the first subject accrued, with 2 of the first 5 subjects being reviewed. Subsequent monitoring will occur in routine intervals per the Winship Data and Safety Monitoring Plan (DSMP).

The DSMC will review pertinent aspects of the study to assess subject safety, compliance with the protocol, data collection, and risk-benefit ratio. Specifically, the Winship Cancer Institute Internal Monitors assigned to the DSMC may verify informed consent, eligibility, data entry, accuracy and availability of source documents, AEs/SAEs, and essential regulatory documents. Following the monitoring review, monitors will provide a preliminary report of monitoring findings to the PI and other pertinent individuals involved in the conduct of the study. The PI is required to address and respond to all the deficiencies noted in the preliminary report. Prior to the completion of the final summary report, monitors will discuss the preliminary report responses with the PI and other team members (when appropriate). A final monitoring summary report will then be prepared by the monitor. Final DSMC review will include the final monitoring summary report with corresponding PI response, submitted CAPA (when applicable), PI Summary statement, and available aggregate toxicity and safety data.

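### The expansion is meant to confirm safety but has no numeric toxicity trigger, and for patients who start on pembrolizumab alone the 21-day DLT window contains no XL888

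*Combined protocol and SAP*

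**What the plan says.** **Aim.** Section 8.1 states: "The aim of the expansion phase is to confirm the safety profile and tolerability of the regimen in patients with pancreatic and colorectal cancer". Sections 2.0 and 3.2 say the same in other words. The expansion is 32 patients, 16 pancreatic and 16 colorectal.

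**Toxicity limits.** Section 8.2, Stopping Rules, reads in full "Not Applicable". Section 5.2.2 acts on two or more DLTs in 3 or 6 subjects, at the escalation dose levels only. Section 2.0 defines the MTD as the dose at which "less than one-third of the subjects experience a DLT in the first 4 weeks of treatment". No section applies that limit to the expansion.

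**DLT window.** Section 5.2.3 counts "definitely treatment related adverse events during the first 21 days of therapy". Section 2.0 uses 4 weeks.

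**Pembrolizumab-alone start.** Section 7.1.2.7 assigns the 16 paired-biopsy patients to begin with pembrolizumab or with the combination for the first cycle, and section 2.0 puts 8 in each treatment cohort. The Day 1 visit text in section 7.1.4 says that "in selected case in patients receiving paired biopsies XL888 will be held in cycle 1". Section 8.1 instead has the PI assign expansion patients generally, with no numbers, and adds: "After the first 3 weeks all patients will receive the combination therapy".

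**Oversight and reporting.** Section 10.5 says: "Depending on the risk level of the protocol, the DSMC review may occur every 6 months or annually". It also provides for team review of the AE and SAE logs. Section 7.2.3 requires SAEs to reach the sponsor within 24 hours. Section 8.3 reports the worst toxicity per patient, with no time limit.

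**The concern.** There are two linked gaps.

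First, the phase meant to confirm safety is larger than the escalation (32 patients against 3 to 18), yet it has no count at which accrual pauses for review. A 3+3 escalation can accept a dose whose DLT rate is above one third, so the expansion is where such an error should show.

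Second, the only defined toxicity window starts at the first dose of any study therapy. For patients who start on pembrolizumab alone, it closes as XL888 begins. If it were carried into the expansion unchanged, these patients would add to the denominator without having been exposed to the combination. One DLT criterion in section 5.2.3, inability to take more than 75% of XL888, cannot be met while XL888 is held. The observed proportion could then fall below one third although the combination rate is above it.

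**Working it through.** **1. The plan's own totals.** Section 8.1 gives 38 to 50 patients. With 32 in the expansion, 6 + 32 = 38 and 18 + 32 = 50, so the totals reproduce. The documents give no safety figure for the expansion. Its alpha and power concern response rate.

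**2. Combination exposure inside the window.** Cycles are 21 days, with XL888 on days 1, 4, 8, 11, 15 and 18. After a pembrolizumab-alone start, XL888 begins on day 22.

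| Window | Days on combination, pembrolizumab-alone start | XL888 doses in window, pembrolizumab-alone start | XL888 doses in window, combination start |
|---|---|---|---|
| 21 days (5.2.3) | 0 of 21 | 0 | 6 |
| 4 weeks (2.0) | 28 − 21 = 7 of 28 | 2 (days 22, 25) | 8 |

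**3. Number affected.** Sixteen biopsy patients, 8 per treatment cohort, give 8 of 32 starting on pembrolizumab alone and 24 starting on the combination.

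**4. Effect if the 21-day window were used in the expansion.** Assume a true combination rate of 40% and no DLTs on pembrolizumab alone.
- Expected proportion: 0.40 × 24/32 = 0.30, below one third.
- Chance of 10 or fewer DLTs in 32 (below one third): binomial P(X ≤ 10; 24, 0.40) = 0.65. With all 32 on the combination it is P(X ≤ 10; 32, 0.40) = 0.20.
- Sensitivity at a true 33%, with 0 to 10% on pembrolizumab alone: (24 × 0.33 + 8 × 0)/32 = 24.8% to (24 × 0.33 + 8 × 0.10)/32 = 27.3%.

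**5. Chance that 3+3 passes a dose with a true 40% rate.**
- If 0/3 suffices: 0.6³ + 3(0.4)(0.6²)(0.6³) = 0.216 + 0.093 = 0.31.
- If six are always treated and at most 1/6 is accepted: 0.6⁶ + 6(0.4)(0.6⁵) = 0.047 + 0.187 = 0.23.

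Section 8.1 supports either reading. The minimum total of 38 implies 3 + 3, while its statement that no DLTs would mean 9 patients fits 3 + 6.

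**6. An illustrative trigger.** Take the limit of one third from section 2.0. The uniform prior, the 0.80 cut-off and looks at 8, 16 and 24 patients are assumptions. Flag at the smallest d with P(p > 1/3) > 0.80 under Beta(1 + d, 1 + n − d):
- n = 8: d = 4 gives 0.855 (d = 3 gives 0.650)
- n = 16: d = 7 gives 0.828 (d = 6 gives 0.674)
- n = 24: d = 10 gives 0.822 (d = 9 gives 0.696)

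Exact chance of at least one flag over the three looks:

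| True DLT rate | 20% | 25% | 30% | 1/3 | 40% | 50% |
|---|---|---|---|---|---|---|
| P(flag) | 0.07 | 0.16 | 0.30 | 0.41 | 0.65 | 0.90 |

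**The case against.** **No diluted rate is planned.** A reader might infer that the expansion will report a DLT rate with unexposed patients in the denominator. The documents do not say so. DLTs serve the escalation and the MTD, and section 8.3 reports worst toxicity with no 21-day limit, so cycle 2 combination toxicity counts. Section 7.1.4 also schedules day 8 and day 15 toxicity visits in cycle 2. This objection stands, so step 4 is conditional. What remains is that the expansion has no defined combination window at all.

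**Review does take place.** A reader might infer that nothing prompts a review until all 32 are treated. That is not supported. Toxicity logs are reviewed, SAEs are expedited, safety reports go to the FDA, and a 6-monthly DSMC review could fall within the expected 12-month enrolment. What is missing is a numeric criterion. DSMC approval is tied to dose escalation, not to continuing the expansion.

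**Half the expansion on the lead-in.** Section 8.1 could be read as 16 of 32, giving 0.40 × 16/32 = 20%. That assumes an even split that no section states. Eight of 32 is better supported.

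**Fewer patients treated.** The illustrative trigger gives a mean of 19 patients treated at a true 40%, against 32. That holds only if every pause becomes a stop and every DLT is known at once, so it should not be claimed as the saving.

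**Exploratory trial.** Section 8.3 calls the analyses hypothesis generating. That argues for a pause-and-review trigger rather than a formal test, but not against having one.

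**Conclusion.** The point holds in this form. The expansion has a stated safety aim, 32 patients and no pre-specified numeric criterion to prompt a review. For patients starting on pembrolizumab alone, the DLT window as written holds either no combination exposure (21 days) or about one week (4 weeks). The two windows conflict, and the number of such patients is 8 of 32 on one reading and unstated on the other.

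The size is moderate. The fall from 40% to about 30% applies only if the 21-day window is used in the expansion, 8 of 32 have the lead-in and pembrolizumab alone causes no DLTs. The 0.31 or 0.23 chance that 3+3 passes a dose with a 40% rate shows why the expansion needs a way to signal excess toxicity. The trigger's limits and probabilities rest on the assumed prior, cut-off and look times, with independent and promptly known outcomes. They illustrate what is possible and are not a derived requirement.

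**What to change.** 1. **Reconcile the text.** Sections 2.0 and 5.2.3 must give one DLT window. Sections 2.0, 7.1.2.7 and 7.1.4 must agree with 8.1 on who may start on pembrolizumab alone and how many. Section 8.1 should also settle how many patients a dose level needs when no DLT occurs.

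2. **Define the expansion's safety analysis.** In sections 8.3 and 8.6, count combination toxicity from each patient's first XL888 dose and tabulate the pembrolizumab-alone cycle separately. All 32 patients can then contribute combination exposure. State whether a DLT proportion will be reported, and its denominator.

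3. **Replace the entry in 8.2** with a pre-specified accrual-pause and DSMC-review trigger for the expansion, tied to the protocol's one-third limit. The sponsor and DSMC should set the numbers; 4/8, 7/16 or 10/24 evaluable patients is one example.

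**Cost.** The change needs wording plus counts from data already collected. The main downside is an unneeded pause when the true rate is below one third: 7% at 20%, 16% at 25% and 30% at 30% for the example. A stricter cut-off would lower these figures and also lower detection above one third. Lead-in patients become evaluable later: about day 42 (21 + 21) with a 21-day window, or day 49 (21 + 28) with a 4-week one.

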### **8.2 Stopping Rules**

Not Applicable

### **8.3 Statistical and Analytical Plans**

Summary statistics will be presented for all safety, efficacy and biomarker parameter analyses. The purpose of these analyses is hypothesis generating and therefore, formal statistical testing will not be performed. Various exploratory statistical tests may be applied to data generated from this trial to generate hypotheses to be tested in subsequent trials. In general, data for continuous parameters will be presented using descriptive statistics including sample size, mean, and median; standard deviation; and minimum and maximum. Categorical parameters (such as pathologic response rate) will be displayed using counts and percentages. Toxicities will be presented as worst toxicity per patient and will be reported as percent toxicity.

### **8.4 Analysis Sets**

All subjects who receive any amount of study drug will be included in the evaluation of safety and efficacy, except for patients who take less than 80% of their prescribed dose of pembrolizumab and/or XL888 since they will be considered inevaluable for the primary endpoint of toxicity.

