### **5.7.2 Subject Replacement Strategy**

Patients who do not complete the intended course of chemotherapy due to reasons other than toxicity will be considered as in-evaluable for the primary endpoint and will be replaced.

[illegible]

Trial Period:	Treatment Cycles a									End of Treatment	Post-Treatment		
Treatment Cycle/Title:	Main Study Screening (Visit 2)	1	2	3	4	5	To be repeated beyond 8 cycles			Discon	Safety Follow-up	Follow Up Visits b	Survival Follow-Up
Scheduling Window (Days):	-28 to -1	± 3	± 3	± 3	± 3	± 3	± 3	± 3	± 3	At time of Discon	30 days post discon ± 7 days	Every 8 weeks post discon	Every 12 weeks
Comprehensive Serum Chemistry Panel	X	X	X	X	X	X	X	X	X	X	X	X	
Fasting triglyceride, cholesterol and glucose	X			X				X					
Urinalysis	X			X				X		X			
T3, FT4 and TSH	X		X			X			X	X	X		
ECG g	X	X	X		X		X g		X g				
Tumor Imaging	X f			X h			X h						
Archival or Newly Obtained Tissue Collection i	X	X											
Correlative Studies Blood Collection j	X	X	X	X						X			

- Treatment cycles are 3 weeks
- Only for patients with ongoing treatment related toxicities
- Pembrolizumab will be given day 1, XL888 twice weekly orally
- ECOG performance status should be done within 10 days or less from day 1 of cycle 1
- Ophthalmologic exam done at baseline and repeated only if there are symptoms
- Baseline imaging with 8 weeks of day 1 is acceptable
- ECG day1 2 to 3 hours after administration of XL888 every other cycle after C2 (C1, C2, C4, C6 etc)
- Scans will be done every 3 cycles between day 15 and day 21
- Paired biopsies will only be obtained from 16 patients on the dose expansion cohort
- Samples will be collected at baseline, day 15, and every cycle for the first 9 weeks. Analysis will include proportion of T, B, NK, memory and effector T cell subsets and expression of PD-1, PD-L1 and B7 family members. Samples will be collected at baseline and on weeks 6 and 9. This will be performed using interferon- gamma and CD107.

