#### **7.1.1.6 Trial Compliance (Medication/Diet/Activity/Other)**

Compliance with XL888 will be determined using drug diary and pill counts performed on day 1 of each cycle. Patients who take less than 80% of their prescribed dose of pembrolizumab and/or XL888 due to reasons other than toxicity will be considered inevaluable for the primary endpoint of toxicity and will be replaced.

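### Section 8.4 drops patients below 80% of either drug whatever the reason, which contradicts 7.1.1.6 and 5.7.2 and leaves some dose-limiting toxicities out of the reported results

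*Combined protocol and SAP*

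**What the plan says.** Three places in the combined protocol and SAP decide who counts, and a fourth defines an event in terms of dose intake.

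- **8.4 Analysis Sets** opens with "All subjects who receive any amount of study drug will be included in the evaluation of safety and efficacy" and continues "except for patients who take less than 80% of their prescribed dose of pembrolizumab and/or XL888 since they will be considered inevaluable" for the toxicity endpoint. It gives no reason for the shortfall and no period over which the 80% is measured.
- **7.1.1.6 Trial Compliance** has the same threshold with a limit: "Patients who take less than 80% of their prescribed dose of pembrolizumab and/or XL888 due to reasons other than toxicity will be considered inevaluable". These patients are replaced.
- **5.7.2 Subject Replacement Strategy** carries the same limit, tied to a treatment course that is not defined: "Patients who do not complete the intended course of chemotherapy due to reasons other than toxicity will be considered as in-evaluable". These patients are also replaced.
- **5.2.3 Dose limiting toxicity** lists as a DLT: "In ability to take more than 75% of XL888 due to toxicity".

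Section 5.2.3 counts DLTs "during the first 21 days of therapy". Section 2.0 defines the MTD by patients who "experience a DLT in the first 4 weeks of treatment".

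**The concern.** Toxicity is the primary endpoint (4.2.1.1). An analysis set that requires at least 80% of both drugs, with no exception for toxicity, selects the patients who tolerated treatment. One DLT criterion is itself low XL888 intake because of toxicity, so the exclusion removes some of the events that the trial exists to count.

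It also works against the tables planned in 8.6, which cover adverse events leading to discontinuation or death, skipped doses, delays and reductions. The patients in those tables are among those most exposed to the exclusion.

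Section 5.7.2 adds a separate difficulty. Progression is not toxicity. A patient who clears the DLT window and later progresses may therefore be classed as inevaluable for the primary endpoint, although the DLT observation is complete.

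**Working it through.** **Inputs.** XL888 is taken on Day 1 (7.1.4.2, Treatment Period) and on Days 4, 8, 11, 15 and 18, so 6 doses per 21-day cycle. Four weeks at two doses per week gives 8. The thresholds are 75% (5.2.3) and 80% (7.1.1.6 and 8.4). Each expansion arm has 16 patients (8.1).

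**The plan's own figure.** Section 8.1 gives a total of 38 to 50. With 32 expansion patients this is 6 + 32 = 38 and 18 + 32 = 50, which reproduces. It contains no allowance for excluded or replaced patients.

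**Step 1: the rules side by side, for a patient below 80% because of toxicity.**
- 7.1.1.6: evaluable.
- 5.7.2: evaluable.
- 8.4: excluded from safety and efficacy.

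**Step 2: overlap with the intake-based DLT criterion.** Share = doses taken / doses planned.
- 21 days: 4/6 = 66.7% is at or below 75% and below 80%; 5/6 = 83.3% is neither.
- 28 days: 6/8 = 75% is at or below 75% and below 80%; 7/8 = 87.5% is neither.

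In whole planned doses over either window, every patient who meets this DLT criterion also meets the 8.4 exclusion. A patient with a different DLT is excluded on XL888 intake only after missing two or more doses.

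The overlap depends on the denominator. In milligrams at 90 mg, four full doses, one missed dose and one dose at 60 mg give (4 × 90 + 60) / (6 × 90) = 420/540 = 77.8%. That is excluded by 8.4 but is not a DLT by intake. Section 8.4 also covers pembrolizumab, which this criterion does not.

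**Step 3: effect on a reported toxicity rate.** If x of n patients are affected and k of them are excluded, the reported rate is (x − k)/(n − k). This assumes nobody else is excluded and nobody is replaced. The documents give no toxicity rate for the combination, so x = 5 of n = 16 is an assumption:
- k = 0: 5/16 = 31.3%
- k = 1: 4/15 = 26.7%
- k = 2: 3/14 = 21.4%
- k = 3: 2/13 = 15.4%
- k = 4: 1/12 = 8.3%

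**Step 4: effect on response.** Assume 3 responders in 16, or 18.8%. If three non-responders are excluded, the rate is 3/13 = 23.1%. If one of the three excluded patients had responded, it is 2/13 = 15.4%. The direction depends on whether the excluded patients respond less.

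**The case against.** The strongest reply is that 8.4 is shorthand. It justifies the exclusion by the patients' inevaluable status for the toxicity endpoint. That status is created in 7.1.1.6 and 5.7.2, and both exempt toxicity. This may well be what was meant. It does not rescue the text, because 8.4 is the only definition of the analysis sets, it names efficacy as well as safety, and it omits the limit.

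Other parts of the reply stand, and they rule out stronger readings that a reader might infer:

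- **That the RP2D decision is corrupted.** Section 5.2.2 counts DLTs among the 3 or 6 patients treated. Section 10.5 has the DSMC receive the relevant safety data for patients entered at a dose level and approve escalation. The documents do not say that these decisions use the 8.4 set.
- **That all, or most, DLT patients are removed.** One missed dose leaves 5/6 = 83.3%, and the patient stays in. Section 5.3.2 makes exceptions to the XL888 delay for Grade 3 fatigue, nausea, vomiting and diarrhea.
- **That the 80% is certainly measured against planned doses.** A dose withheld under 5.3.2 might not count as prescribed. Section 8.4 does not settle this.
- **That 5.7.2 requires 24 months of treatment.** Section 5.7 gives 24 months or 35 administrations as a limit on treatment, and Section 1.0 estimates a 6-month average. Neither defines the course in 5.7.2. Dropping patients who cleared the window would also raise the apparent DLT rate, the opposite direction to 8.4.
- **That a stated power is lost.** Section 8.1 gives no response count as a decision rule, and 8.3 says there will be no formal testing.

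**Conclusion.** The concern holds as a contradiction with consequences for reporting. Section 8.4 excludes patients whom 7.1.1.6 and 5.7.2 keep. Counted in planned doses over the DLT window, it excludes everyone who meets the intake-based DLT criterion. Followed literally, the reported toxicity rates are biased downward.

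The size cannot be derived from the documents. In the illustration, 31.3% becomes anything from 26.7% to 8.3% as one to four of the five affected patients are excluded, and 15.4% with three. Any upward bias in response is conditional on lower response among the excluded patients. Escalation may be unaffected if 7.1.1.6 governs it. The point should still be settled before analysis, because as worded the set used to report the primary endpoint leaves out some of that endpoint's own events.

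**What to change.** Rewrite 8.4 as three sets:

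1. **Safety:** all patients who receive any dose of either drug, with no adherence exclusion.
2. **DLT-evaluable:** every patient with a DLT, whatever dose was taken, plus patients without a DLT who complete the DLT window with adequate dosing as the sponsor defines it. Only patients without a DLT who miss doses for reasons unrelated to toxicity are inevaluable and replaced.
3. **Efficacy:** all treated patients.

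State the period for the 80% (the DLT window or all treatment) and its denominator: planned or prescribed, doses or milligrams. Say how biopsy patients whose XL888 is held in cycle 1 are counted.

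In 5.7.2, tie evaluability for the primary endpoint to the DLT window in place of the undefined treatment course. The window itself must first be reconciled between 5.2.3 (21 days) and 2.0 (4 weeks). The sponsor should also reconcile the 75% and 80% figures across 5.2.3, 7.1.1.6 and 8.4. Because 75% is part of a DLT criterion, this review does not propose a value.

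The cost is wording in the protocol and SAP only. Reported toxicity may look less favourable.
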